2.7. SAFETY DATA

SAEs and non-serious adverse reactions for the randomised population will be listed. SAEs for the registry population will also be listed.

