7. PARTICIPANT ELIGIBILITY CRITERIA

7.1 Inclusion Criteria

For the Screening Log (no follow-up envisaged nor linkage to electronic medical records)

- 1. ≥18 years
- 2. Heart failure in the investigators opinion (new onset or decompensated chronic heart failure)
- 3. Planned to receive >80mg/day of furosemide or equivalent* (IV, SC, or oral) in the next 24 hours.
- 4. Worsening symptoms & signs of congestion in the prior10 days requiring at least **one** of the following:
 - a) hospitalisation
 - b) administration of intravenous diuretics
 - c) an increase in the dose of loop diuretic by at least 40mg/day of furosemide (or equivalent**) to a total of at least 80mg/day of furosemide (or equivalent*)
 - d) addition of a thiazide diuretic to treatment with a loop diuretic

Version 5.0 22 July 2021 Page 25 of 82

- * a dose of 80mg/day of furosemide is considered equivalent to 2mg/day of bumetanide or 20mg/day of torasemide.
- ** a dose of 40mg/day of furosemide is considered equivalent to 1mg/day of bumetanide or 10 mg/day of torasemide.

For the Consented Registry (with linkage to electronic medical records)

- 1. Fulfils the criteria for the screening log
- 2. Able and willing to provide written informed consent for registry participation

For Randomised Trial Run-in

- 1. Fulfils criteria for the consented registry
- 2. Clinical diagnosis of heart failure for at least 4 weeks
- 3. Congestion as shown by at least one of the following:
 - a) Peripheral oedema
 - b) Raised venous pressure
 - c) Inferior vena cava diameter >20mm
- 4. Cardiac dysfunction documented by at least **one** of the following in the previous three years:
 - a) A LVEF<50% or a report of moderate or severe left ventricular dysfunction
 - b) Left atrial diameter >3.0cm/m2 (body surface area)
 - c) Elevated BNP or NT-proBNP
 - i. BNP >150ng/L if in sinus rhythm or >450ng/L if not in sinus rhythm
 - ii. NT-proBNP >500ng/L if in sinus rhythm and >1500ng/L if not in sinus rhythm
- 5. Able and willing to provide written informed consent for the randomised trial

For Randomisation

- 1. Serum potassium >5.0mmol/L
 - Patients with a serum potassium >5.0mmol/L may be randomised immediately unless they have severe hyperkalaemia requiring, in the investigators opinion, intravenous treatment or a potassium binding agent.
 - Severe hyperkalaemia should be managed according to the UK Renal Association guidelines of 2014 (https://renal.org/wp-content/uploads/2017/06/hyperkalaemia-guideline-1.pdf).

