8.1.2 Schedule of Procedures for the Randomised Trial (long-term follow-up)

		Majority of care at follow-up in clinic									
Visit	T7	T8	T9	T10	T11	T12	T13	T14	TX	EOS	
Months	3	6	9	12	15	18	21	24	+3		
Window +/- days	14	14	14	14	14	14	14	14	14	NA	
Consent											
History											
Symptoms/NYHA	Х	Х	Х	Х	Х	Х	Х	Х	Х	Х	
PGA	Х	Х	Х	Х	Х	Х	Х	Х	Х	Х	
CV Therapy	Х	Х	Х	Х	Х	Х	Х	Х	Х	Х	
Non-CV Med		Х		Х				Х			
Height											
Weight	Х	Х	Х	Х	Х	Х	Х	Х	Х	Х	
Vital Signs	Х	X*	Х	Χ*	Х	Х	Х	Χ*	Х	Х	
Physical Exam											
Oedema Grade	Χ	X	X	X	X	X	X	X	Х	X	
Orthopnoea Test		X		X				X			
ECG trace											
Electronic ECG		X		X				X			
Echocardiogram		Opt		Opt				Opt			
Haematology		X		X				X			
Biochem Safety	Χ		X		Χ	X	Χ		X	X	
Biochem+		Х		X				X			
Spot Urine		X		Х				Х			
Biomarkers		Х		Х				Х			
KCCQ/EQ5D		Х		Х				Х			
Walk Test @		Х		Х				Х			
Titration/Compliance	Χ	Х	X	X	Χ	Χ	Χ	X	X	X	
AE/ SAE	Х	Х	Х	Х	Х	Х	Х	Х	X	X	
Dispensing	Χ	X	X	X	Χ	Х	Χ	X	Х		

T = titration visit. TX = repeat visits every 3 months for dispensing and titration. EOS = end of trial. CV = cardiovascular. X* vital signs measured during orthopnoea (orthop) test. Opt = optional

KCCQ = Kansas City Cardiomyopathy Questionnaire. EQ5D = EuroQol 5-dimension questionnaire. NYHA = New York Heart Association functional class. PGA = patient global assessment on a 7-point scale ranging from much worse to much better.

@ for patients who feel unable to do these tests, the reason will be recorded. AE / SAE = adverse / serious adverse events.

Key visits for the assessment of clinical efficacy and endpoints are

- Day 7 (+/-3 days or discharge from hospital or day-care)
- Day 60 (+/-14 days)
- And at 6 months (+/-14 days) months,12 months (+/- one month) and 24 months (+/- one month)

Additional visits are required to assess symptoms and safety (serum potassium/magnesium, renal function, blood pressure). Patients may be evaluated in the community or clinic setting as convenient but will have to attend hospital visits to obtain trial IMP (patiromer, spironolactone/eplerenone).

In addition, if doses of patiromer or MRA are changed, blood pressure and serum electrolytes and creatinine should be re-checked both after 7-12 days and after 30-45 days. If the patient becomes acutely unwell for any reason, blood pressure, serum electrolytes and creatinine should be re-checked. Serum potassium should also be checked within 48 hours of stopping patiromer.

Version 5.0 22 July 2021 Page 30 of 82

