10.2 Operational reporting for (S)AEs

Adverse events (AEs) will be recorded, notified, assessed, reported, analysed and managed in accordance with the Medicines for Human Use (Clinical Trials) Regulations 2004 (as amended) and this protocol. All AEs occurring during the trial that are observed by the Investigator or reported by the participant will be recorded in the participant's medical records whether or not attributed to trial medication.

All adverse reactions must be recorded within the eCRF.

All Serious Adverse Events (SAEs) occurring during the trial must be recorded in the eCRF.

The following are not considered be to be SAEs for the purposes of this trial.

- Routine treatment or monitoring of heart failure not associated with deterioration in heart failure.
- Treatment which was elective or pre-planned, for a pre-existing non-cardiac condition not associated with any deterioration in heart failure, e.g. pre-planned hip replacement operation which does not lead to further complications.
- Treatment on an emergency, outpatient basis for an event not fulfilling any of the definitions of serious as given above and not resulting in hospital admission.
- Admissions for social reasons not associated with a deterioration of heart failure.

All SAEs will be reported to the IDMC and analysed as part of the final trial results.

Full details of SAEs will be recorded in the electronic Case Report Form. The following information will be collected:

- full details in medical terms and a case description
- event duration (start and end dates, if applicable)
- action taken
- outcome
- · seriousness criteria
- causality (i.e. relatedness to trial drug / investigation), in the opinion of the investigator
- if related, whether the reaction would be considered expected or unexpected.

Any change of condition or other follow-up information should be added to the eCRF as soon as it is available or at least within 24 hours of the information becoming available. Events will be followed up until the event has resolved or a final outcome has been reached.

Assessment of Adverse Events

All adverse events must be assessed for seriousness. All SAEs must also be assessed for severity, causality and expectedness with reference to this protocol and the Reference Safety Information (RSI).

Version 5.0 22 July 2021 Page 54 of 82

Assessment of seriousness

An adverse event will be considered serious if it:

- results in death
- is life threatening

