1.6. STATISTICAL ANALYSIS PLAN (SAP)

1.6.1. SAP OBJECTIVES

The objective of this SAP is to describe the reporting of the RELIEHF trial which was closed early with only 4 participants randomised.

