2. ANALYSIS

2.1. STUDY POPULATIONS

The screened population will consist of all patients screened, who met the inclusion criteria. The registry population will consist of all patients who consented to participate in the registry. The run-in population will consist of patients who consented to enter the randomised trial, who usually required a run-in phase to allow serum potassium to increase to >5.0 mmol/L. The randomised population consists of participants who were randomised.

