2.5. RUN-IN DATA

For those who entered the run-in phase, the following information (recorded at the start and end of run-in) will be reported (summary table and listing):

- Weight
- SBP
- Type of MRA given
- Total daily dose of MRA given
- Serum sodium
- Serum potassium
- Serum creatinine
- Urea

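### SAP 2.7 plans no listing of non-serious adverse reactions in run-in patients who received trial MRA but were not randomised, although their SAEs are listed

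*SAP*

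**What the plan says.** SAP 2.7 sets two safety outputs. First, "SAEs and non-serious adverse reactions for the randomised population will be listed". Second, "SAEs for the registry population will also be listed". The first covers four people: SAP 1.6.1 describes the "RELIEHF trial which was closed early with only 4 participants randomised".

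SAP 2.1 defines a further group: "The run-in population will consist of patients who consented to enter the randomised trial". SAP 2.5 gives those who entered run-in a summary table and listing of weight, systolic pressure, MRA type and dose, sodium, potassium, creatinine and urea, "recorded at the start and end of run-in". Adverse reactions are not among the items.

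Protocol 10.2 states: "All adverse reactions must be recorded within the eCRF". It does not limit this to randomised patients. Protocol 10.1 defines an adverse reaction by its relation to any dose of an IMP given to the participant.

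**The concern.** Run-in is a period of protocol-directed treatment with a trial drug. Protocol 9.7 and section 8 have the MRA started or increased for up to 35 days, with spironolactone reaching as much as 100 mg/day, in patients whose potassium has not exceeded 5.0 mmol/L. Only those who then exceed that level can be randomised. Patients who stop short of randomisation have taken trial MRA, and any whose potassium did exceed 5.0 mmol/L may have taken the patiromer test dose as well.

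If the non-serious reaction listing is produced exactly as SAP 2.7 is written, nothing from these patients appears in it. SAP 1.6.3 explains the reduced reporting by the four randomisations. That is a good reason to drop formal analyses. It does not explain leaving other drug-exposed patients out of a plain listing. At stake is whether the close-out report accounts for all the reactions that the protocol says must be recorded.

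**Working it through.** No sample size, power or event figure is involved, so the check sets the two documents side by side.

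1. **Is run-in MRA a trial drug?** Yes. Protocol 9.1 describes spironolactone and eplerenone under the investigational products, and 8.1.2 has patients attending hospital to "obtain trial IMP (patiromer, spironolactone/eplerenone". Protocol 9.6 allows ward stock for in-patients during run-in. That changes the supply route, not the status of the drug.

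2. **Is patiromer given before randomisation?** Yes, to some. Protocol 7.1 and 9.7 require a single 8.4 g test dose once potassium exceeds 5.0 mmol/L. Section 8 adds that the full dose need not be consumed.

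3. **Does the duty to record depend on randomisation?** Not in 10.1 or in the recording rule of 10.2. Protocol 10.9 follows events and reactions until 30 days after the last IMP dose.

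4. **Which SAP outputs reach a run-in patient who was not randomised?**

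| Item | Planned output | Covers this patient? |
|---|---|---|
| SAEs, including serious reactions | SAP 2.7, registry listing | Yes |
| Systolic pressure, potassium, creatinine, MRA dose at start and end of run-in | SAP 2.5 | Yes |
| Reason for not progressing | SAP 2.2 | Yes |
| Non-serious adverse reactions | SAP 2.7, randomised population only | No |

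The first row follows from Protocol 7.1, where the first run-in criterion is "Fulfils criteria for the consented registry". Run-in patients are therefore registry patients.

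5. **Were the data collected?** Uncertain. In the Protocol 8.1.1 schedule, as extracted from the PDF, the SAE row is marked from the run-in column and the AE row only from Day 1. The table header is broken in extraction, so column positions need checking against the PDF. If that reading is right, non-serious reactions were not prompted for at run-in contacts, which sits badly with the rule in 10.2.

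6. **How many patients?** The documents give four randomised and no count for run-in, so the number exposed but not randomised cannot be stated.

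**The case against.** The strongest reply is that little is lost. Serious reactions are listed through the registry. Protocol Appendix 1 names hyperkalaemia, symptomatic hypotension and renal dysfunction as the MRA hazards, and SAP 2.5 reports potassium, systolic pressure and creatinine for everyone who entered run-in. SAP 2.2 reports why patients did not progress. This stands, and it limits the point to non-serious reactions.

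A second reply is that SAP section 4 promises listings of all derived datasets. It does not say what those datasets contain, and 2.7 is the specific rule for safety data, so this does not close the gap.

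A third is that Protocol 10.2 assigns causality for each IMP the participant is randomised to receive, wording that does not fit events before randomisation. It governs how causality is assigned and does not cancel the recording rule, but it is another reason to doubt that run-in reactions were captured consistently. Similarly, a blank schedule cell shows when events are reviewed at visits and need not override 10.2. The two passages should be reconciled rather than treated as a proven contradiction.

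The reply that a new listing could mislead also has force. If collection was patchy before Day 1, few entries would not mean few reactions. That calls for a note beside the listing, not for leaving it out.

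**Conclusion.** The point holds in a limited form. Non-serious adverse reactions in run-in patients exposed to trial MRA, and in some cases to a patiromer test dose, have no planned listing unless the patient was one of the four randomised. This rests on reading SAP 2.7 as written and on Protocol 10.1 and 10.2 applying to any IMP dose. It is a modest reporting gap in a descriptive close-out plan and affects no formal analysis.

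Three stronger readings are tempting and unsupported:

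- *A reader might infer that all reactions in these patients are missed.* They are not: serious ones fall within the registry SAE listing.
- *A reader might infer that run-in makes up most of the trial's drug exposure.* No run-in numbers or durations are given. As an illustration, assume each of the four was followed for between 60 days and 15 months, the last numbered month in SAP 2.6. That is 4 × 60 = 240 to about 4 × 457 ≈ 1,830 patient-days. Matching it would take 240/35 ≈ 7 to 1,830/35 ≈ 52 full-length run-ins. Either is possible.
- *A reader might infer that the restriction understates harm because only patients who tolerated titration were randomised.* The direction is not established. Uncorrected eGFR below 30 ml/min/1.73m², systolic pressure below 90 mmHg or severe hyperkalaemia needing treatment kept patients out, which points that way. But randomisation itself required potassium above 5.0 mmol/L, and patients who never reached it were excluded (Protocol 7.1 and 7.2), which for hyperkalaemia points the other way.

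**What to change.** - **SAP 2.7:** list non-serious adverse reactions for the run-in population as well as the randomised population. The SAP 2.1 definition rests on consent to the trial, so it would also include anyone who took a test dose without needing MRA titration.
- **Protocol 8.1.1 and 10.2:** check the AE row against the PDF and reconcile it with the recording rule. If reactions during run-in were not systematically collected, say so beside the listing.
- **SAP 2.5 (optional):** add calculated eGFR. It can be derived from the creatinine already reported, and SAP 2.4 already calculates it by CKD-EPI for the screening and registry data. Highest potassium during run-in is worth adding only if values between the start and end of run-in were recorded.

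The cost is one listing, one explanatory sentence and, if wanted, one derived variable. The risk is that a sparse listing is misread, which the note addresses. Nothing in trial conduct or treatment changes.

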3. TABLES

Dummy reports will be produced and reviewed by the chief investigator. Approval of the content of the final report will be documented prior to database lock.

4. LISTINGS

Listings of all derived datasets will be produced as excel spreadsheets.

5. DOCUMENT HISTORY

This is the first version of the SAP, initial creation.
